1.0. Background

1.1. Myeloid neoplasms are diseases of aging

MN are a group of diseases that include acute myeloid leukemia (AML), myelodysplastic syndrome (MDS), MDS/myeloproliferative neoplasm (MPN) overlap, chronic myelomonocytic leukemia (CMML), and atypical chronic myeloid leukemia (aCML).¹ Over 60% of MN are diagnosed in adults aged \geq 60 years.^{2,3} For fit older patients with AML (i.e., without significant comorbidities or disabilities), the standard first-line treatment consists of intensive inpatient chemotherapy. Intensive chemotherapy provides the best chance for durable remission, but it is associated with a high treatment-related mortality (60-day mortality: 15-20%).^{4,5} Intensive therapy is utilized in <1% of older patients with AML seen in the community oncology setting, due to various reasons such as distance to tertiary centers and need for hospitalizations.⁶ In the last decade, lowintensity outpatient treatments with reduced treatment-related mortality rates, such as hypomethylating agents (HMA), have become available.^{7–9} These treatments have permitted more older patients with AML, including those with comorbidities and disabilities, to receive leukemia-directed therapy.¹⁰ Furthermore, given the recent FDA approval of HMA combination therapy for AML (e.g., HMA and venetoclax), which has similar or better efficacy than intensive therapy,¹¹ HMA-based therapies will be used more widely in older patients with AML. For older patients with other MN requiring chemotherapy, HMA are often the treatment of choice.¹² Thus, HMA are now standard of care for older patients with MN. HMA are typically given continuously until progression, death, or stem cell transplant.

1.2. Even with HMA, a high percentage of older patients with MN experience physical function decline and symptoms (e.g., fatigue, mood disturbances).

In prior studies, up to 98% of older patients with MN receiving intensive chemotherapy experience physical function decline and symptoms.^{13–15} Our group and others have also shown that 73% of older patients with MN receiving HMA had impairments in physical function and 33% reported mood disturbances.^{16,17} Physical function decline and symptoms can lead to reduced quality of life (QoL), treatment interruptions, and shorter survival.^{13,18–22} Therefore, it is imperative to develop interventions for older patients receiving HMA that prevent physical function decline and improve symptoms so that they can maintain their QoL and continue to receive cancer treatments.

1.3. Older patients with MN can exercise and may derive benefits from exercise.

Exercise may prevent physical function decline and improve symptoms.^{23–26} Older adults can derive benefits from exercise even if they only maintain or minimally improve physical activity from baseline.²⁷ A previous systematic review has shown that exercise is safe in frail older adults.²⁸ Three pilot studies evaluated exercise in 50 older patients with MN (only one receiving HMA was included) and showed that they can exercise and that it was safe. In addition, exercise improved physical function, fatigue, mood disturbances, and QoL.^{29–31} In our own pilot work, older patients with MN receiving HMA reported

Protocol Version: 22OCTOBER2021

walking at least an average of 2k-3k steps/day, which is comparable to prior exercise studies in older patients with solid tumors, suggesting that they have similar exercise capacity. Overall, our pilot data and prior studies suggest that older patients with MN can exercise safely and may benefit from it, but exercise interventions tailored to this population are limited.³²

1.4. Exercise for Cancer Patients (EXCAP):

[name] (co-investigators) developed EXCAP, an individually tailored, low- to moderate-intensity, home-based walking and progressive resistance exercise program designed for patients with cancer and delivered by an exercise physiologist. By design, EXCAP is tailored to the physical capacity of patients with cancer. Our data from >300 older patients undergoing active cancer treatments from 4 phase 2/3 studies demonstrated that they were able to perform the walking (average steps walked/day=4k-11k at post-intervention) and resistance exercises (15-22 min/day, 2-4 days/week).^{23,27,33,34} EXCAP also improved physical function, fatigue, and mood in patients with solid tumors.^{35–37} In older patients with solid tumors, we have shown that EXCAP improved physical function (measured using the Short Physical Performance Battery, SPPB), mood, and QoL, but effect sizes were small (Cohen's d=0.10-0.30).^{23,27,38} Older patients had lower exercise adherence than their younger counterparts (average steps walked/day=4k vs. 5k at post-intervention).

1.5. The use of a mobile health (mHealth) application (app) may improve exercise adherence in older patients with MN.

Exercise adherence can be a challenge in older patients with MN due to comorbidities, symptoms, lack of exercise self-efficacy, and limited access to exercise oncology professionals and facilities.^{39–42} mHealth has the potential to improve exercise adherence by enhancing exercise self-efficacy and by helping to address barriers to exercise in real time.^{43,44} In our systematic review of studies in the cancer population, however, we found that older patients with MN are rarely included in mHealth exercise studies.⁴³

1.6. PointClick Care Mobile App:

We have worked with a mHealth company (PointClickCare, formerly TouchStream) to upgrade an app (TouchStream) for monitoring older patients (12 had MN) receiving cancer treatment.¹⁶ Our pilot data suggest that the app is usable and feasible (Table 1). I conducted interviews with 16 patients to elicit barriers and facilitators for adaptation of the app and revision of the study protocol. Patients indicated their willingness to exercise and preferred a structured exercise program in combination with the app over physicians' recommendations to exercise without a structured program and app.

1.7. Several mechanisms are associated with physical function decline, fatigue, and mood disturbances.

Potential mechanisms include inflammatory dysregulation, neuroimmunological changes, energy imbalance, and skeletal muscle changes (e.g., mitochondrial dysfunction, decline in neural function, reduced satellite cell function, defects in calcium homeostasis);^{45,46} these are often inter-related.^{47,48} Inflammatory dysregulation, in particular, has strong mechanistic evidence because of its association with frailty in older adults^{49,50} and because it can affect virtually every biological system (the most relevant are the muscular, cardiovascular, and cerebrovascular systems).⁴⁵

1.8. Tumor necrosis factor (TNF) α and related inflammatory cytokines are associated with physical function decline, fatigue, mood disturbances, and worsening QoL in older patients with MN.

TNF α is involved in early inflammatory responses and is regarded as the "master regulator" of inflammation.^{51,52} Preclinical studies demonstrate that cancer and chemotherapy increase serum TNF α and related cytokine levels [e.g., interleukin-1 β (IL-1 β), interleukin-6 (IL-6), interleukin-8 (IL-8)].^{53–55,56(p),57} Activation of TNF α and related cytokine pathways leads to physical function decline, fatigue, and mood disturbances,^{58–62} which are abrogated by inhibition of these pathways.^{62,63} In older adults with MN, we have shown that higher baseline serum TNF α levels were associated with shorter survival. In patients with MN, our group and others also found that increased serum TNF α , soluble TNF receptor 1 (sTNFR1), and related cytokine levels were associated with physical function decline, fatigue, mood disturbances, and worsening QoL.^{64–66} Exercise reduces inflammation, which may explain how exercise prevents physical function decline and improves fatigue and mood disturbances.^{67,68}

1.9. Understanding exercise-induced changes in the TNF α and related cytokine pathways may help to tailor exercise prescriptions for older patients with cancer in clinical practice.

In patients with higher serum TNF α levels, a lower dose of exercise may be sufficient to decrease serum TNF α levels and prevent physical function decline. However, the epigenetic regulation of TNF α in the context of exercise is not well characterized. DNA methylation is an epigenetic mechanism that can be stably inherited throughout cell divisions.⁶⁹ DNA methylation is the addition of methyl groups to the DNA molecule at the CpG sites where a cytosine nucleotide is followed by a guanine.⁷⁰ DNA methylation of the *TNF* α gene promoter region decreases *TNF* α gene and protein expression.^{71,72} Prior studies have shown that exercise increases *TNF* α gene promoter methylation and decreases *TNF* α gene and protein expression.^{73–76} A better understanding of the TNF α and related cytokine pathways can identify biomarkers to help tailor exercise prescriptions.

To summarize, we chose the TNF α pathway as our translational focus because 1) our preliminary data showed that higher serum TNF α and soluble TNF receptor 1 levels were associated with physical function decline, mood disturbances, and shorter survival;⁶⁴ 2) exercise increases *TNF* α gene promoter methylation and decreases *TNF* α gene and protein expression;^{73–76} 3) it will allow us to expand our preliminary data and explore other TNF α related cytokine pathways (e.g., IL-1 β , IL-6, IL-8); and 4) we have the

Protocol Version: 22OCTOBER2021 Page 7 of 54

expertise to reliably measure, analyze, and interpret $TNF\alpha$ gene promoter methylation and $TNF\alpha$ gene and protein expression in a clinical trial.⁷⁷ While we focus on older patients with MN, this population serves as a model for studying an individually tailored mHealth exercise intervention among vulnerable older patients receiving prolonged cancer treatments to prevent physical function decline and improve symptoms. Findings from our studies will inform research and practice for a large proportion of older patients who are currently understudied in behavioral intervention trials. This work is also highly novel and may lay the foundation for the use of biomarkers in the design of behavioral interventions to improve outcomes in older patients with cancer.

Summary of knowledge/Proposed Solution:

No mHealth exercise intervention is currently available for older patients with MN receiving outpatient chemotherapy, specifically HMA. TNF α and related cytokines are associated with physical function decline, fatigue, and mood disturbances. Based on our expertise and prior studies, we propose to integrate the content of EXCAP into the PointClick Care app to enhance older patients' adherence to exercise and to understand exercise-induced changes in physical function, fatigue, mood, QoL, and TNF α and related cytokine pathways.

The mobile app and EXCAP have been studied individually in previous studies.^{16,23,33,34,78} In this study, we plan to combine them for older patients with MN receiving outpatient chemotherapy including HMA.

2.0. Aim and Hypothesis

2.1. Primary Aim

To develop a mobile app delivery platform integrating EXCAP and adapt its content, format, and delivery for older patients with MN receiving HMA using feedback from 15 patients.

2.2. Secondary Aim

To assess the feasibility of a mobile health exercise intervention (GO-EXCAP Mobile App) over 8 ± 4 weeks in a single-arm pilot study in 25 patients with myeloid neoplasms receiving outpatient chemotherapy (including HMA).

2.3. Exploratory Aim

To examine relationships among $TNF\alpha$ and related cytokine gene promoter methylation and gene and protein expression.

2.2.1. Hypothesis

The GO-EXCAP Mobile App will be feasible in older patients with myeloid neoplasms receiving outpatient chemotherapy.

2.2.1. Feasibility metrics

The feasibility of the GO-EXCAP Mobile App will be evaluated based on the following:

a) Percentage of patients wearing the activity tracker and entering resistance exercise data into the mobile app.

b) Percentage of patients performing both walking and resistance exercises during the study period days.

c) Recruitment rates (percentage of patients who are approached and agree to enroll).

d) Retention rates (percentage of patients who are enrolled and complete postintervention assessments).

3.0. Study Design and Population

3.1. Study Settings

Wilmot Cancer Institute (WCI), University of Rochester Medical Center (including WCIaffiliated community practices such as Interlakes Oncology, Dansville, Pluta, Olean, Wellsville)

3.2. Study Type Aim 1: Qualitative study

Aim 2: Single-arm pilot study

3.3. Study Population

Aim 1: We will obtain feedback from 15 older patients receiving HMA. Our planned sample size (N=15) will allow us to achieve thematic saturation.^{79,80} To obtain 15 patients, we will consent up to 20 patients to account for screen fail or withdrawal.

Aim 2: We will recruit 25 older patients receiving outpatient chemotherapy (see Section 8.2.2 for sample size justification). To obtain 25 patients, we will consent up to 45 patients to account for screen fail or withdrawal.

3.4. Inclusion and Exclusion Criteria

Inclusion criteria

- Age ≥ 60 years (conventional definition of older age in clinical trials of MN)⁸¹⁻⁸³
- Have a diagnosis of MN
- Receiving outpatient chemotherapy (e.g., HMA)
- English speaking
- Eastern Cooperative Oncology Group (ECOG) performance status of 0-2
- No medical contraindications for exercise per oncologist
- Able to walk 4 meters as part of Short Physical Performance Battery measured walk (with or without assistive device)
- Able to provide informed consent

Exclusion criteria

• Platelet count of 10,000 per microliter or less in the most recent blood draw (due to risk of spontaneous bleeding) prior to transfusion (i.e., patients are allowed to enroll if their platelet count is 10,000 per microliter or less but is scheduled to receive transfusion the day of consent)

Each subject's eligibility will be documented on redcap. This will be printed and signed and dated by the principal investigator.

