4.1. Identification of Study Subjects, Recruitment, and Consent Procedures

Study subjects will be identified in multiple ways. First, patients will be identified by their treating physician, the nurses that work with the physicians, and the study coordinator. The study coordinator will work closely with the physicians and nurses to identify those patients that are anticipated or have begun treatment with chemotherapy. Second, with permission from oncology providers, we will screen for eligible patients from clinic schedules. The study coordinator contacts the physician (or their designee) and informs them that a patient may be eligible for the study. The physician (or their designee) then confirms if the patient is a study candidate or not (including whether they are a candidate to exercise). This will be documented in the subject research chart. If there is a question about eligibility, the principal investigator will be contacted and will meet with the patient, review the medical records, and perform an assessment of eligibility if necessary. The same identification process will be used for all sites.

For in-person consent, below are the possible scenarios for obtaining consent.

- 1) Physician/Study Investigator makes the initial contact andprovides consent form, and patient signs consent with the physician on the same day: After confirming with the physician (or their designee) that a patient is a potential candidate for the study, the study staff will provide a consent form to the treating physician/study investigator so he/she can provide it to the patient during an in-person clinic visit. The physician/study investigator will go over every detail of the study during the clinic visit with patient. If agrees, the patient will sign the consent form with the physician/study investigator during the same in-person visit.
- 2) Study staff makes the initial contact and provides consent form, and patient signs consent with the study staff on the same day:

After confirming with the physician (or their designee) that a patient is a potential candidate for the study, the patient will be provided with an informed consent form by the study staff when they come in for an in-person clinic visit. The study staff will introduce the study to the patients and go over every detail of the study. If agrees, the patient will sign the consent form with the study staff during the same in- person visit with the study staff.

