4.1.4. Participation

Current state, federal, and institutional regulations concerning informed consent will be followed. Participation in this study is voluntary. Participants are free not to take part or to withdraw at any time, for whatever reason, without risking loss of present or future care they would otherwise expect to receive. In the event that a patient does withdraw from the study, the information they have already provided will be kept in a confidential manner. Participants may discontinue participation in the study at any time if they decide they do not wish to take part any longer. Participants may be withdrawn from the study by research personnel if it is deemed in their best interest to no longer participate.

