The second component of the exercise program is an individually tailored therapeutic resistance band exercise prescription designed to provide low to moderately intense progressive resistance exercise [3-5 exercise rating of perceived exertion (RPE) on the ACSM revised rating scale] 7 days a week. Subjects are given a set of 3 color-coded therapeutic resistance bands representing varying levels of resistance. The exercise physiologist will explain the proper use of the resistance bands, safety, and the appropriate mechanics for performing the resistance training exercises. Subjects are instructed to begin with an individually determined number of sets (1 set = 8-15repetitions) for each of the sixteen exercises at a moderately challenging level (RPE=3-5) 7 days a week. The exercises target the upper and lower body. The exercise physiologist will work with the subject to find an optimally challenging number of sets and repetitions with the appropriately colored resistance band for each exercise with each patient. Subjects are instructed to increase the intensity by changing to a different color band or by shortening the initial length of the band for increased resistance. They are encouraged to progressively increase from their individual baseline sets and repetitions to a maximum of 4 sets of 15 repetitions for each exercise daily over the course of the 8-week (± 4 weeks) intervention at a rate that is optimally challenging. The therapeutic resistance band exercise prescription will be developed and individually tailored for each subject by the exercise physiologist. Each subject will report the intensity of their resistance exercise using 1) the rated perceive exertion (RPE) scale and 2) time spent for resistance band exercise by entering these data directly on the tablet.

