6.3. GO-EXCAP Mobile App

We plan to integrate the content of the EXCAP exercise program into the PointClick Care mobile app (Figure 5). Older patients will participate in the EXCAP exercise program and enter exercise data into the mobile app. In addition, they will complete a symptom inventory and enter any barriers to exercise into the mobile app weekly. The study team (physiologist) logs into the web portal 2x/week to monitor intervention adherence, provide feedback, and adjust exercise prescriptions. These recommendations are available to the patients - they are automatically displayed via the mobile app daily. Patients can interact with the physiologist directly or via the mobile app.

Symptom reporting and management is an important component of our intervention because symptoms are common barriers to exercise. Based on our pilot data,^{16,90} we selected 15 common symptoms experienced by patients with MN based on the Patient-Reported Outcomes version of the Common Terminology Criteria for Adverse Events (PRO-CTCAE).⁹¹ We will assess symptoms weekly. These symptoms will be recorded on the web portal (described above). Study coordinator will log on to the web portal at least weekly to ensure that the symptom surveys are being completed. If the symptom surveys are not completed, the study coordinator will remind the patient during the weekly calls. For each symptom, we will use standardized severity-based algorithms and self-management strategies based on established protocols (Figure 6).^{92–94} A symptom report will be generated at clinic visits. In addition, these reports will be provided to the clinic nurses on a weekly basis.

Therefore, the mobile app serves as a tracking, teaching, and self-management device that is tailored to the individual. We will adapt the intervention content, format, and delivery of the app based on feedback from patients.

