7.0. Treatment Protocol

7.1 Study Outline

Patients who receive HMA and other outpatient chemotherapy typically have declines in their blood counts during the 1st month of therapy before improvements are noted. Therefore, we will initiate our intervention at cycle 2 the earliest. HMA and other common chemotherapy are administered daily as an infusion or subcutaneous injection for 5-10 days every 4 weeks. There are outpatient chemotherapy that are pill-based as well (e.g., enasidenib, ivosidenib) and are also dosed every 4 weeks. We will consent patients and they will complete measures during routine visits. They will complete baseline measures during the 4th week of a chemotherapy cycle up to day 1 of the subsequent cycle prior to chemotherapy administration (study week 0) (Figure 1). The intervention will start during the 1st week of of a new cycle (study week 1) and will last 8 ± 4 weeks. The post-intervention measures will be completed 2 cycles later during the 4th week of the cycle (study week 8 ± 4). To illustrate this, if the intervention starts in cycle 2 week 1, baseline measures will take place on cycle 1 week 4, and postintervention assessment will place on cycle 3 week 4. If the intervention starts in cycle 6 week 1, baseline measures will take place on cycle 5 week 4, and post-intervention assessment will place on cycle 7 week 4.

At the screening visit, we will confirm if the patient is eligible using the eligibility criteria above. Once we confirm their eligibility, we will obtain either in-person or verbal consent. The patient will then complete a demographic questionnaire that asks about the participant's age, gender, race, ethnicity, education level, marital status, employment status, and Eastern Cooperative Oncology Group (ECOG) performance status as well as their cancer and treatment characteristics (see Section 7.2).

For Aim 1, one interview will be conducted with each participant in a private space for approximately 30 minutes. First, we will explain the rationale and demonstrate the use of the GO-EXCAP Mobile App. Second, we will elicit preferences for the content, format, and delivery of the intervention (Table 2). Collectively, the findings will be used to adapt the intervention.

Feature	Goal	Example of Adaptation

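### The platelet exception enrolls Aim 2 patients at or below 10,000 per microliter on a scheduled transfusion, with no later count required to pass that limit before strength testing or home exercise

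*Combined protocol and SAP*

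**What the plan says.** All references are to the combined protocol and SAP.

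- **Exclusion (Section 3.4).** The only exclusion criterion is "Platelet count of 10,000 per microliter or less in the most recent blood draw (due to risk of spontaneous bleeding) prior to transfusion".
- **Exception (same sentence).** "patients are allowed to enroll if their platelet count is 10,000 per microliter or less but is scheduled to receive transfusion the day of consent". The criteria form one list for both aims, so the exception applies to Aim 2.
- **Clearance.** Section 3.4 also requires "No medical contraindications for exercise per oncologist". In Section 4.1, before consent, "The physician (or their designee) then confirms if the patient is a study candidate or not (including whether they are a candidate to exercise".
- **Exertion.** Section 7.2.6 includes a handgrip test and an isokinetic test, both at maximal effort. Section 9.1 allows either to be omitted in some settings. The home resistance program in Section 6.1 is milder: "designed to provide low to moderately intense progressive resistance exercise", at a perceived exertion of 3 to 5.
- **Blood count.** Sections 7.2.4 and 9.1 have a complete blood count (CBC) abstracted from the medical record at baseline and after the intervention.

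**The concern.** The sponsor set a numeric floor on top of the oncologist's judgment and gave bleeding as the reason. The exception lifts that floor on the strength of an appointment. A scheduled transfusion may not be given, and one that is given may not bring the count above the limit. Patients who enter this way are the only participants whose qualifying count lies in the range that the protocol itself calls too risky, and they are the ones for whom the limit is never checked again.

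In Aim 2 these patients may go on to maximal-effort testing and weeks of unsupervised exercise at home. Low counts are to be expected here: Section 7.1 says that counts typically fall in the first month of therapy and that chemotherapy is commonly delayed by cytopenias. Section 10.1.1 names muscle strain and tripping as possible exercise injuries and does not mention bleeding.

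**Working it through.** The protocol gives no figure to reproduce, and no formula applies. The check is whether any provision between consent and exertion restores the limit for a patient admitted through the exception.

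**Order of events in Aim 2**

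1. Physician confirmation of candidacy, then consent, with a transfusion scheduled that day (Sections 3.4 and 4.1). Consent may be given by telephone and the tracker mailed, so study staff need not be in the clinic on the transfusion day.
2. Step tracking for 4 to 7 days (Section 7.1). Section 4.1 describes in-person assessments as generally taking place at a second visit, after the tracker has been supplied.
3. Baseline measures in study week 0, which Section 7.1 defines as week 4 of a chemotherapy cycle up to day 1 of the next, before that day's chemotherapy. Section 9.1 places the CBC and the strength tests here.
4. Home exercise from study week 1, the first week of the new cycle.

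Exertion therefore normally comes days after consent. A transfusion booked for the consent day, even if given, does not show what the count is when the patient is tested or starts to exercise.

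**Each safeguard against the missing requirement**

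- *Oncologist and physician clearance (Sections 3.4 and 4.1).* Clinical judgment. The Section 4.1 confirmation precedes consent, so it cannot reflect the result of a transfusion still to come.
- *Exercise readiness form (Section 7.2.3.5).* A general questionnaire with no count requirement stated.
- *Timing (Section 7.1).* "Therefore, we will initiate our intervention at cycle 2 the earliest". This avoids the usual first-month fall but sets no platelet value.
- *Baseline CBC (Sections 7.2.4 and 9.1).* Falls in week 0, before the first home session, but no value is required and no action follows from it.
- *Omission of in-person tests for safety (Sections 7.2.3 and 9.1).* Permitted, not required, and not linked to platelets. The note on choosing the cancer center over the exercise laboratory removes isokinetic testing but not handgrip.
- *Physiologist present at isokinetic testing (Section 7.2.6).* Concerned with form and comfort.
- *Weekly app questions, twice-weekly physiologist review and weekly calls (Section 7.1).* These run during the intervention. The app questions cover new contraindications but rely on self-report, and the example given is cardiac.
- *Symptom reports (Section 6.3).* "these reports will be provided to the clinic nurses on a weekly basis". They concern symptoms, not counts.
- *Withdrawal (Section 4.1.4).* "Participants may be withdrawn from the study by research personnel if it is deemed in their best interest". Discretionary.

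Section 3.4 is the only place where a platelet value or a transfusion is a condition of anything. No provision requires that the transfusion be completed or that a later count exceed 10,000 per microliter.

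**The case against.** The strongest reply is that exercise suitability belongs to the treating oncologist, that many checks surround it, and that the stated reason for the limit is spontaneous bleeding and not bleeding on exertion. No text says that a count just above 10,000 makes maximal testing acceptable, so using the entry limit as a start limit is partly a clinical preference. A patient who enrolls slightly above the limit and then falls below it is also unchecked. Much of this stands: the limit is a minimum, clearance must still govern, and clinicians may well look at the count in practice. It does not explain why the protocol applies its own limit to everyone except those known to be at or below it.

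Three stronger readings are tempting and are not supported.

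- *A reader might infer that no count is available before exercise.* The week 0 schedule puts an abstracted CBC ahead of the week 1 start. What is missing is a threshold and an action.
- *A reader might infer that such a patient is tested or exercises on the day of consent.* The 4 to 7 days of tracking and the usual second visit point the other way.
- *A reader might infer that holding such a patient would distort the retention or adherence results.* Section 3.3 allows up to 45 consents to obtain 25 patients, with screen failures expected, and Section 5.3 enrolls those who are eligible. A patient stopped before starting fits that provision.

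**Conclusion.** The gap is real and narrow. An Aim 2 patient admitted through the exception can reach strength testing (isokinetic or handgrip, where performed) or the first home session with no recorded count above the limit that Section 3.4 sets. The general safeguards lower the risk but do not check the criterion.

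The size of the risk cannot be stated, since neither the frequency of the exception nor a bleeding rate is given. The text does not support a claim that harm is likely. The conclusion rests on the wording alone and assumes that no separate operating procedure supplies the check. It is a safety correction that should be made because it is specific and inexpensive. It does not affect the validity of the feasibility analysis.

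**What to change.** Reword the exception in Section 3.4 for Aim 2:

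- A patient at or below 10,000 per microliter may consent on the day of a scheduled transfusion. Neither strength testing nor the first home session may take place until the most recent chart CBC, drawn after that transfusion and within the week 0 baseline window, shows platelets above 10,000 per microliter. Tying the count to week 0 matters: a value taken shortly after the transfusion could otherwise qualify a patient who exercises many days later.
- Record the value and draw date on the eligibility form that Section 3.4 already requires to be signed.
- State that passing this minimum does not replace the oncologist's exercise clearance.
- Handle a patient who does not meet it as a screen failure under Section 3.3.

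No step is added for patients above the limit at consent.

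The cost is one clause and one form entry. Because the CBC is already abstracted at baseline, an extra draw is needed only when the chart holds none in the right window. Some patients may become screen failures. Others may miss the window and wait for the next cycle, about 4 weeks, possibly repeating baseline measures. How often this would happen cannot be estimated from the protocol.
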